Clinical Project Manager	[name] [name] Gustave Roussy Direction de la Recherche Clinique Service Promotion des Etudes Cliniques	[contact] [contact] [name] [contact]
Sponsor Clinical Study Coordinator	[name] Gustave Roussy Direction de la Recherche Clinique Service Promotion des Etudes Cliniques	[contact] [contact] [contact]

SYNOPSIS - PROTOCOL N° (2335/2015)

EudraCT number EUCT number	2015-00546 2024-515678		Version and Da	ate	6.1	Decem	ber 18 th , 2023							
Title	A phase II study to assess the efficacy of the anti-PD-L1 antibody atezolizumab (MPDL3280A) administered with stereotactic ablative radiotherapy (SABR) in patients with metastatic tumours													
Abbreviated title	SABR-PDL1 Phase II													
Sponsor	Gustave Roussy [name]													
Coordonnating	[name]													
Investigator														
Number of centers	Total	Total 6 France 4 International : 2 Spain:												
Indication		Patients with metastatic tumours (colorectal cancer, non-small lung cancer, renal cell carcinoma or sarcoma)												
Primary objective			ar progression-f b therapy using			der combi	ined SABR and							
	• in pa	atients with	n metastatic cold	rectal ca	ancer (close	d to inclus	sions)							
	• in pa	atients with	n metastatic non	-small lu	ung cancer (d	closed to	inclusions);							
	• in pa	atients with	n metastatic ren	al cell ca	arcinoma (clo	sed to in	clusions);							
	• in pa	atients with	n metastatic sard	coma (cl	losed to inclu	ısions)								
Secondary Objectives		PDL1 atez					ombined SABR odified RECIST							
	and the r	non-irradia		ed on tu	mour respon		radiated lesions tors and clinical							
	who can	not receive		radiation	n dose or re	lative atea	tion of patients zolizumab dose mg).							
	- To evalu	ate the to	cicity of atezoliz	umab in	combination	with SAE	3R according to							

	the NCI-CTCAE scale (version 4.03).
	 To investigate the safety profile using NCI CTC-AE 4.03 scale following the second SABR course in combination with atezolizumab of tumor lesions after progression in patients with lung cancer and sarcoma.

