Primary evaluation criterion	One year-Progression-free survival rate is defined as the rate of patients alive and free of progression at one year. Progression is defined using RECIST 1.1. criteria, or death, whatever the cause of death, whichever occurs first.
Secondary	Efficacy:
evaluation criteria	Progression-free survival (PFS) measured from the date of treatment initiation to date of progression or death whichever comes first. Patients alive and free of progression at the cut-off date will be censored at the last assessment date
	Tumour response indicators and clinical endpoints, assessed according to RECIST v 1.1 and modified RECIST are:
	- Disease Control Rate (DCR): complete responses (CR) + partial responses (PR) + stable disease (SD).
	- Objective Response Rate (ORR): CR + PR
	- Duration of response (DOR)
	- Time to progression of non-irradiated lesions is computed as the delay from enrollment to the first occurrence of progression outside of the irradiated field
	- Time to progression of irradiated lesions is computed as the delay from enrollment to the first occurrence of progression of irradiated lesions;
	- Evaluation of the local control, distant control.
	Toxicity: NCI- CTCAE V4.03 scale Toxicity is adverse events graded with the NCI-CTC-AE v4.03 scale, at least possibly related to the treatment.
	For patients with lung cancer and sarcoma receiving a second SABR course for oligoprogression:
	- Progression-free survival 2 (PFS2) measured from the date of second SABR course to date of second progression or death whichever comes first. Patients alive and free of progression at the cut-off date will be censored at the last assessment date.
	- Tumor response indicators and clinical endpoints, assessed according to RECIST v1.1 at 6 weeks after the second SABR course.
	Time to progression ratio (TTPr) in patient receiving a second SABR course:
	- To define the TTP ratio, let's denote:
	 TTP1 the time from treatment initiation to the time of progression after first irradiation
	TTP2 the time from first progression to the time of progression after the second SABR course. Due to the very poor prognosis of those patients, death without documented progression will be counted as progressions. Patients alive and free of progression at the cut-off date will be censored at the last assessment date. Radiological progression is measured using RECIST v1.1 on the same tumor lesions over all the

	trial, whenever p	possible.									

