5 TREATMENTS

5.1 Identification of the study treatments

5.1.1 Atezolizumab

Formulation, Packaging, and Handling

Atezolizumab drug product is provided in a single-use, 20-mL USP/Ph. Eur. Type 1 glass vial as a colorless to slightly yellow, sterile, preservative-free clear liquid solution intended for IV administration. The vial is designed to deliver 20 mL (1200 mg) of atezolizumab solution but may contain more than the stated volume to enable delivery of the entire 20 mL volume. The atezolizumab drug product is formulated as 60 mg/mL atezolizumab in 20 mM histidine acetate, 120 mM sucrose, 0.04% polysorbate 20, pH 5.8.

Atezolizumab must be refrigerated at 2°C–8°C upon receipt until use.

Atezolizumab vials should not be used beyond the expiration date provided by the manufacturer. No preservative is used in the atezolizumab drug product; therefore, each vial is intended for single use only. Vial contents should not be frozen or shaken and should be protected from direct sunlight.

For further details, see the atezolizumab Investigator's Brochure.

Dose Solution Preparation and Storage:

Dose preparation will be done on the day when atezolizumab is administered.

Atezolizumab is administered only using 250 mL 0.9% sodium chloride saline IV bags and infusion lines equipped with 0.2 μ m in-line filters. Bags may be constructed of polyvinyl chloride (PVC) or polyolefin (PO); the IV infusion line may be constructed in PVC or polyethylene; and the 0.2 μ m in-line filters may be constructed in polyethersulfone (PES).

The required volume of atezolizumab for a patient is 20 mL. No dilution of the vial contents is required.

Atezolizumab Drug Product should be held at room temperature for 30 minutes prior to removal from the vials.

Dose solutions are prepared by removing 20 mL of saline solution from the IV bag prior to the addition of 20 mL of atezolizumab Drug Product. The IV bags containing atezolizumab should be mixed and handled gently. Once the atezolizumab dose solution is prepared, it may be stored at 2°C–8°C (36°F–46°F) and/or at room temperature for up to 8-hours prior to the start of infusion. However, if the infusion is interrupted and the combined storage and dose hold time of the diluted IV bags exceeds the 8-hour limit, prepare a new dose solution to resume the infusion.

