5.1.2 Stereotactic Ablative Radiation Therapy (SABR)

SABR will be administered concurrently during the second cycle of the anti-PD-L1 Atezolizumab (week 4) and in case of first progression in patients with lung cancer and sarcoma.

SABR will be delivered using 6MV photons or other energies with standard field encompassing tumour. Hypofractionated SABR will be delivered within 3 fractions in total to a total of 45 Gy (3 fractions of 15 Gy). In order to comply with the QUANTEC normal tissue tolerance guidelines, the dose may be adapted according to dosimetric constraints but must never be inferior to 33 Gy in fractions of 11 Gy.

Tumour size will be ≤ 4 cm according to recent imaging (CT, MR or PET).

The radiation dose will be prescribed to the 90% isodose line in order to deliver 95% of the planned dose to 95% of the planned tumour volume (PTV).

Patients will be eligible if dose constraints to organ at risk are respected.

SABR software tools and accurate dose calculations allow for better targeting of tumours, while providing motion management for precise dose delivery. Generally, this technique includes:

- 4D CT data integration for moving target such as lung tumours
- Patient's immobilization with a vacuum cushion.
- Precise type B dose calculation algorithm (Monte Carlo, or other type B dose calculation algorithms)
- Monitoring of respiratory motion.
- Real-time detection and compensation of tumour motion (on-board CT)

The definition of volumes will be in accordance with ICRU Reports #50, #62 and #83.

SABR will be given on alternate days and only type B dose calculation algorithms will be accepted.

Margins from GTV (or ITV) to PTV are of 5 - 10 mm to account for set-up error and organ motion.

Any organ that is traversed by part or all of a beam should be contoured so that the dose it receives can be assessed. Organs should be outlined by the treating radiotherapist (or dosimetrist and checked by treating radiotherapist). Dose constraints are adapted to the standard recommendations (cf Appendix 1: Rules for SABR administration according to tumour location).

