5.3 Adaptation of doses and interruption of treatment

5.3.1 Doses modifications for SABR

Management of treatments during protocol treatment toxicity according to the NCI-CTCAE scale (CTCAE v 5.0)

Cutaneous toxicity (radiotherapy-associated dermatitis)

- Grade 4, SABR must be discontinued

Pulmonary toxicity (dyspnea, pneumopathy)

- **Grade 3/4,** SABR and atezolizumab must be interrupted. Patients must then be reassessed every week

SABR must only be discontinued in the event of a grade or 3 or 4 pharyngo-oesophageal, cutaneous or pulmonary reaction in the irradiated field. SABR and/or atezolizumab must only be reintroduced after the toxicity has recovered to grade 2 or less.

Digestive toxicity within the field:

Medical management includes treating diarrhea, dehydration, malabsorption, and abdominal or rectal discomfort. Symptoms usually resolve with medications, dietary changes, and rest. If symptoms become severe despite these measures, a treatment break may be warranted.

In addition to these medications, opioids may offer relief from abdominal pain. If proctitis or oesophgitis is present, steroid foam given rectally may offer relief from symptoms.

If esophagitis occurs, making oral feeding impossible, placement of a nasogastric tube must be considered.

In the event of grade 3 esophagitis that is poorly tolerated in spite of appropriate treatment, SABR can either be continued with enteral and/or parenteral feeding plus appropriate analgesic treatment, or it may be discontinued for less than 5 days until improvement (≤ grade 2 or grade 3 that is well tolerated with appropriate treatment).

- Grade 4 (oesophagitis, diarrhea, abdominal pain), SABR and atezolizumab must be interrupted. Patients must then be reassessed every week
- **Grade 3 (diarrhea, abdominal pain),** Atezolizumab must be discontinued only if symptoms do not improve despite discontinuation of SABR for 8 days.

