7.2.2 Safety

Toxicity is assessed according to the NCI- CTCAE V4.03 scale during physical examination Identified risks as well as potential risks associated with atezolizumab are extensively described in the Investigator Brochure.

Toxicity is the adverse events graded with the NCI-CTC-AE v4.03 scale, at least possibly related to the treatment.

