8.3.3 Safety Analysis

All included subjects who take at least 1 dose of the atezolizumab will be included in the safety analyses. Adverse events will be summarized by worst severity grade. AEs, as well as treatment-emergent AEs, will be summarized by system organ class, and preferred term. Atezolizumab-related adverse events, adverse events leading to death or to discontinuation from treatment, events classified as NCI-CTCAE v4.0 Grade 3 or Grade 4 (or moderate/severe if other rating scale is used), atezolizumab-related events, and serious adverse events will be summarized separately.

Cross tabulations will be provided to summarize frequencies of abnormalities.

By-subject listings will be provided for all relevant safety data.

Graphical displays and figures will be provided where useful to assist in the interpretation of results especially blood pressure handling.

Descriptive analysis will be described for:

- Deaths,
- SAEs.
- AE drop-outs,
- AEs.

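### The related-event summary in section 8.3.3 counts only atezolizumab-related events, so it is narrower than the toxicity endpoint in section 7.2.2, which covers atezolizumab with SABR

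*Protocol*

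**What the plan says.** The endpoint is defined twice in nearly the same words. Section 7.2.2 has "Toxicity is the adverse events graded with the NCI-CTC-AE v4.03 scale, at least possibly related to the treatment", and the secondary evaluation criteria in the synopsis have "Toxicity is adverse events graded with the NCI-CTC-AE v4.03 scale, at least possibly related to the treatment". Neither text limits the relationship to the drug. Section 2.2 gives the matching objective as the toxicity of atezolizumab in combination with SABR. The section headed "5.1 Identification of the study treatments" has two entries, atezolizumab in 5.1.1 and SABR in 5.1.2.

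Section 8.3.3 sets out the analysis. It summarises adverse events by worst grade, and adverse events and treatment-emergent adverse events by system organ class and preferred term. One sentence then lists the subsets to be tabulated on their own. It begins with "Atezolizumab-related adverse events, adverse events leading to death or to discontinuation from treatment", goes on to grade 3 or 4 events, and ends with "atezolizumab-related events, and serious adverse events will be summarized separately". By-subject listings are also promised. The section names no summary of SABR-related events or of events related to the combination.

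**The concern.** The endpoint asks what the combined treatment may have caused. The named summary asks what atezolizumab may have caused. The two differ by the events that an investigator attributes to SABR and not to the drug, and the protocol expects such events: section 5.3.1 has rules for radiotherapy dermatitis, oesophagitis and any grade 3 or 4 "pharyngo-oesophageal, cutaneous or pulmonary reaction in the irradiated field".

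An analysis that follows 8.3.3 literally would produce one related-event table, and readers would take it as the related toxicity of the combination. It would understate that toxicity by the SABR-only events. The all-cause tables are an imperfect substitute, because in progressing metastatic disease they mix toxicity with events due to the disease.

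**Working it through.** There is no figure to reproduce, and no sample size or error rate is involved. The check compares the definitions and then follows individual events through the planned outputs.

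**Step 1: what each text counts.** Let A be the events at least possibly related to atezolizumab and S the events at least possibly related to SABR.

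- Endpoint (7.2.2 and synopsis, read with 2.2 and 5.1): A or S.
- Named relatedness summary (8.3.3): A.
- Difference: events in S but not in A.

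An event attributed to both treatments is in A and is counted. Only SABR-only events fall out.

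**Step 2: relatedness items in the 8.3.3 sentence.** Atezolizumab-related: 2. SABR-related: 0. Related to the combination or to study treatment: 0.

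**Step 3: two example events, each attributed to SABR alone.**

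| Output in 8.3.3 | Grade 2 in-field dermatitis, not serious, SABR completed | Grade 3 in-field oesophagitis that stops SABR |
|---|---|---|
| All adverse events, worst grade | yes | yes |
| Treatment-emergent, by class and term | yes | yes |
| Atezolizumab-related (both mentions) | no | no |
| Grade 3-4 | no | yes |
| Leading to discontinuation from treatment | no | yes, if stopping SABR counts as discontinuation |
| Serious | no | only if it meets a seriousness criterion |
| By-subject listing | yes | yes |

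Both events meet the 7.2.2 definition, and neither reaches the related-event table. The first is visible only in the all-cause outputs and the listing.

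**Step 4: effect on patient-level counts.** For a count of patients with any related event, a patient is missed only if every related event that patient had was SABR-only. For a table by preferred term or worst grade, a patient can also be missed under one term, or shown at too low a grade, when the SABR-only event is the worst one.

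**Step 5: size.** The shortfall is the number of patients affected as in step 4, divided by the safety population (at least one dose of atezolizumab). The protocol gives no rate of SABR-only events, so no number can be put in. SABR is part of the planned treatment in all four cohorts, so the gap is not confined to one of them.

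**Step 6: decisions that depend on the table.** None were found. The stopping rule in 8.2 counts any toxicity of grade 4 and above, and any toxicity that interrupts treatment for more than two cycles. It does not draw on the 8.3.3 summary.

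**The case against.** The strongest reply has three parts.

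First, listing the same summary twice makes no sense as a deliberate choice, so this is an editorial slip and not a choice of analysis. That is probably right, and it is why the point is minor. It does not remove the point, because an SAP written from 8.3.3 could carry the narrower category forward.

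Second, section 8.3.1 says that categorical endpoints will be summarised by number and percentage. Toxicity as defined in 7.2.2 is a secondary criterion, and 8.3.3 does not say that its list is complete. A treatment-related table could therefore be produced under 8.3.1. This reading is possible, but a general sentence does not clearly override a section that names its relatedness category, and names it twice.

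Third, no event is lost. This stands in full. A reader might infer that SABR toxicity goes unreported, and the protocol does not support that: the all-cause summaries and the listings hold every event, and the more severe ones also reach the grade 3-4, serious-event or discontinuation summaries. In addition, with concurrent treatment and a threshold of at least possible relationship, SABR-only attribution may be limited to clear in-field reactions.

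**Conclusion.** The point holds as a minor inconsistency. The relatedness summary named in 8.3.3 is narrower than the endpoint in 7.2.2 by the events attributed to SABR alone. This rests on reading the treatment in 7.2.2 as atezolizumab with SABR, which sections 2.2 and 5.1 support, and on following 8.3.3 literally. That the repeated phrase is a slip is inference. The size cannot be stated. The effect is on descriptive reporting only; the primary endpoint and the stopping rule are untouched.

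A reader might also infer that 8.3.3 leaves the safety objective for re-irradiated patients without an analysis, since the synopsis aims "To investigate the safety profile using NCI CTC-AE 4.03 scale following the second SABR course in combination with atezolizumab of tumor lesions" and 8.3.3 does not mention that course. The protocol does not support this as a fault. Section 8.3.3 is silent on the second course and states nothing wrong about it. A table by treatment period for a subset is commonly left to the SAP, and the pooled summaries and listings already include those events.

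**What to change.** In section 8.3.3, replace the second mention of atezolizumab-related events with: *events at least possibly related to study treatment (atezolizumab and/or SABR)*. The first mention can stay as the drug-specific subset. The related-event summary then matches 7.2.2 and answers the objective in 2.2.

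The text change itself costs almost nothing. Section 9.2.1 already captures relationship to study drug or treatment for serious events and events of special interest. The possible cost lies with the other events. All cohorts are closed to inclusions, so if the CRF did not record SABR attribution for non-serious events, it would have to be assigned retrospectively in an open-label trial, which is often uncertain. If that is not feasible, keep the present table, label it atezolizumab-related only, and state that it is narrower than the definition in 7.2.2.

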9 SERIOUS ADVERSE EVENTS

9.1 Definition

9.1.1 Adverse Event (AE)

An Adverse Event (AE) is any new untoward medical occurrence or worsening of a preexisting medical condition in a patient or clinical investigation subject administered an investigational (medicinal) product. An AE can therefore be any unfavourable and unintended sign (including abnormal laboratory findings for example), symptom, or disease temporally associated with the use of a medical product, whether or not a causal relationship (i.e. related/not related) with the treatment is suspected.

Any unfavorable and unintended sign (including an abnormal laboratory finding), symptom, or disease temporally associated with the treatment, whether or not considered related to study treatment.

Any deterioration in a laboratory value or other clinical test (e.g., ECG, X-ray) that is associated with symptoms or leads to a change in study treatment or concomitant treatment or discontinuation from study treatment.

9.1.2 Serious Adverse Event (SAE)

A Serious Adverse Event (SAE) is any untoward medical occurrence that at any dose:

- Is fatal (results in death)
- Is life-threatening
- Requires or prolongs in-patient hospitalization

- Results in persistent or significant disability / incapacity
- Is a congenital anomaly / birth defect
- Is medically significant (defined as any clinical event or laboratory result that may not be immediately life-threatening or result in death or hospitalization but, based upon appropriate medical and scientific judgment, may jeopardize the subject or may require intervention (eg,medical, surgical) to prevent one of the other serious outcomes listed in the definition above. Examples of such events include but are not limited to, allergic bronchospasm requiring intensive treatment in an emergency room or at home, blood dyscrasia or convulsions that do not result in inpatient hospitalization, development of drug dependency or drug abuse, transmission of an infectious agent.

Although overdose and new cancer are not always serious by regulatory definitions, these events should be reported on a SAE report form and sent to the sponsor in an expedited

A SAE judged as potentially related to a study drug qualifys as Serious Adverse Drug Reaction (SADR).

The following are not considered to be serious adverse events (SAE):

- Events exclusively related to tumour relapse / progression or treatment of tumour relapse / progressions are not considered as SAE,
- A visit to the emergency room or other hospital department for less than 24 hours that does not result in admission (unless considered an "important medical event" or a lifethreatening event),
- Outpatient or same-day or ambulatory procedures,
- Observation or short-stay units,
- Hospitalization due to diagnostic procedures or standard supportive care (e.g. implant of central venous catheter),
- A pre-planned hospitalization for a condition which existed at the start of study drug and which did not worsen during the course of study drug treatment,
- Social admission (e.g., subject has no place to sleep; hospice facilities),
- Administrative admission (e.g., for yearly physical examinations),
- Protocol-specified admission during a clinical trial (e.g., for a procedure required by the study protocol or for clinical research),
- Optional admission not associated with a precipitating clinical AE (e.g., for elective cosmetic surgery).

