 - Patients who have received prior treatment with anti-CTLA-4 may be enrolled, provided at least 5 half-lives (approximately 75 days) have elapsed from the last dose of anti-CTLA-4 to the first dose of atezolizumab and there was no history of severe immune-mediated adverse effects from anti-CTLA-4 (NCI CTCAE Grade 3 and 4)
- 20. Treatment with systemic immunostimulatory agents (including but not limited to interferon-alpha (IFN- α) and interleukin-2 (IL-2) within 4 weeks or five half-lives of the drug (whichever is shorter) prior to Cycle 1, Day 1

Study Treatment

Drug: The anti-PD-L1 antibody atezolizumab will be administered at a dose of 1200 mg every 3 weeks.

Atezolizumab treatment will be administered as long as:

- Patients are experiencing clinical benefit (as assessed by an investigator), and
- In the absence of unacceptable toxicity or symptomatic deterioration attributed to disease progression after an integrated assessment of radiographic data, biopsy results (if available) and clinical status.

In case of progressive disease according to RECIST v1.1 criteria, patients will be permitted to continue atezolizumab treatment if they meet all of the following criteria:

- Evidence of clinical benefit as assessed by the Investigator,
- Absence of symptoms and signs (including worsening of laboratory values, e.g., new or worsening hypercalcemia) indicating unequivocal progression of disease.
- No decline in ECOG performance status that can be attributed to disease progression, and
- Absence of tumour progression at critical anatomical sites (e.g., leptomeningeal disease) that cannot be managed by protocol-allowed medical interventions.

SABR: SABR will be delivered concurrently with the 2nd cycle of atezolizumab (at week 4) using 6MV photons or other energies with standard field encompassing tumour. If oligoprogression occurs, a second course of SABR is allowed while continuing atezolizumab (patient with lung cancer and sarcoma).

At least one tumour site will receive radiation and another tumour site(s) should be

	avaluable by PECIST v4.4
	evaluable by RECIST v1.1.
	Hypofractionated SABR will be delivered at a dose of 45 Gy in 3 fractions of 15 Gy (equivalent biologic dose (BED) > 80 Gy). The recommended fractionation is 45 Gy (3 fractions of 15 Gy) but shall be adapted upon normal tissue tolerance constraints. Total duration of radiotherapy must not exceed eight days. Tumour size will be ≤ 4 cm according to recent imaging (CT or PET).

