In patients with lung cancer and sarcoma and in case of first progression defined using RECIST 1.1, a second SABR course can be delivered with the same conditions.

[figure not shown]

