9.2.1 Reporting of Serious Adverse Events (SAE)

Any SAE/AESI which occurs or comes to the attention of the investigator at any time during the study since consent is given and within 90 days after the last administration of study drug/treatment, independent of the circumstances or suspected cause, must be reported immediately, via my eclinical, a web portal that allow electronic transmission of SAEs /AESIs, https://myeclinical.evedrug.eu/form/IGR/login.php or if it's not possible by fax using a SAE report form at [name] :

Pharmacovigilance unit

[contact]

(9 a.m. - 6 p.m. from Monday to Friday, except on bank holidays)

E-mail: [contact]/[contact]

All late Serious Adverse Events/AESIs (occurring after this period of 90 days) considered to be reasonably related to the study treatment(s) or the research must be reported (no time limit).

Information collected in the SAE form is crucial to assess the case. For this reason, diligence in collecting as much verifiable and reliable information is needed: both, quality and timeliness are key factors. If known, the diagnosis of the underlying illness or disorder should be recorded, rather than its individual symptoms. The following information should be captured for all SAEs/AESIs: onset, duration, intensity, and seriousness, relationship to study drug/treatment, action taken and treatment required.

The investigator must also attach the following to the serious adverse event report form, wherever possible:

- A copy of the summary of hospitalization or prolongation of hospitalization
- A copy of the post-mortem report (if applicable)
- A copy of all relevant laboratory examinations and the dates on which these examinations were carried out, including relevant negative results, as well as normal laboratory ranges.
- All other document that he judges useful and relevant.

All these documents will remain anonymous.

Further information can be requested (by e-mail, fax, telephone or when visiting) by the monitor and/or the safety manager.

Follow-up information

The investigator is responsible for the appropriate medical follow-up of patients until resolution or stabilization of the adverse event or until the patient's death. This may mean that follow-up should continue once the patient has left the trial.

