9.2.2 Reporting of (Non-Serious) Adverse Events of Special Interest (Study Specific AESI)

There are certain types of AE that are considered of study specific importance (AESI). These AEs are summarized below and must be reported in an expedited manner (immediately after learning of the event) by using my eclinical report or if not possible the SAE form, even if they do not meet the criteria for seriousness (check the box 'medically significant' and specify 'Non-Serious Adverse Event of Special Interest').

Adverse events of special interest for this study include the following:

- Pneumonitis
- Hypoxia or dyspnea Grade ≥ 3
- Myocarditis (any grade) and other cardiac disorders grade ≥ 2
- Autoimmune mediated pericardial disorders including pericarditis, pericardial effusion and cardiac tamponade
- Colitis
- Endocrinopathies: diabetes mellitus, pancreatitis, adrenal insufficiency, thyroiditis (hypo or hyperthyroidism), hypophysitis
- Hepatitis
- Pancreatitis

- Transaminitis: Grade \geq 2 (AST or ALT > 3 × ULN AND total bilirubin > 2 × ULN) or AST/ALT > 10 × ULN
- Systemic lupus erythematosus
- Neuropathies: Guillain-Barré syndrome, Myasthenic syndrome, Myasthenia Gravis, Meningoencephalitis
- Immune-related Nephritis
- Events suggestive of hypersensitivity, cytokine release syndrome, influenza-like illness, systemic inflammatory response syndrome, systemic inflammatory activation or infusion-reaction syndromes, Hemophagocytic lymphohistiocytosis or macrophage activation syndrome
- Cases of potential drug-induced liver injury that include an elevated ALT or AST in combination with either an elevated bilirubin or clinical jaundice, as defined by Hy's law
- Suspected transmission of an infectious agent by the study drug, as defined below:
 - Any organism, virus, or infectious particle (e.g., prion protein transmitting transmissible spongiform encephalopathy), pathogenic or non-pathogenic, is considered an infectious agent. A transmission of an infectious agent may be suspected from clinical symptoms or laboratory findings that indicate an infection in a patient exposed to a medicinal product. This term applies only when a contamination of the study drug is suspected.
- Immune-related myopathies includingrhabdomyolysis
- Vasculitis
- Myositis
- Autoimmune haemolytic anaemia
- Severe cutaneous reactions (e.g., Stevens-Johnson syndrome, dermatitis bullous, toxic epidermal necrolysis)
- Ocular toxicities (e.g. uveitis, retinitis, optic neuritis)
- Myelitis

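### The SAE definition excludes events due only to treatment of progression, so a serious toxicity of the protocol's own second SABR course can be classed as not an SAE

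*Protocol*

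**What the plan says.** Section 9.1.2 gives the usual seriousness criteria and then a list of exclusions. The first reads: "Events exclusively related to tumour relapse / progression or treatment of tumour relapse / progressions are not considered as SAE". No qualifier separates treatment given under the protocol from treatment given outside it.

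Section 3.1 makes a second SABR course part of the trial in the lung cancer and sarcoma cohorts: "in case of first progression defined using RECIST 1.1, a second SABR course can be delivered with the same conditions". The Synopsis (Study Treatment) adds that atezolizumab goes on at the same time: "If oligoprogression occurs, a second course of SABR is allowed while continuing atezolizumab (patient with lung cancer and sarcoma". Section 5.1.2 describes SABR, including its use at first progression, among the study treatments.

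The Synopsis makes the safety profile, graded by CTCAE 4.03, a secondary objective "following the second SABR course in combination with atezolizumab of tumor lesions after progression in patients with lung cancer and sarcoma".

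Section 9.2.1 requires that any SAE or AESI, "independent of the circumstances or suspected cause, must be reported immediately", with a window running from consent until "within 90 days after the last administration of study drug/treatment". Section 9.2.2 puts a list of AESIs on the same expedited route "even if they do not meet the criteria for seriousness". Section 8.3.3 says that "atezolizumab-related events, and serious adverse events will be summarized separately".

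**The concern.** An exclusion for treatment of progression is harmless where trial treatment ends at progression, because later therapy then belongs to someone else's regimen. Here, in two cohorts, the treatment of first progression is itself a study intervention whose safety the trial sets out to describe. An investigator who applies section 9.1.2 as written can conclude that a hospitalisation caused only by the second SABR course is not an SAE.

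At stake are the expedited report to the sponsor, the assessments that start from that report, and the SAE summary. Sites may also differ in how they read the clause, which would make SAE counts after the second course depend on the site.

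**Working it through.** The point rests on the text. The only arithmetic is the size of the exposed group.

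**1. Does the second SABR course fall under the exclusion?** Section 9.1.2 removes events whose sole cause is progression or treatment of progression. Section 3.1 triggers the second course by a first RECIST 1.1 progression. The course is therefore treatment of progression, and no exception for protocol treatment is written. A serious event caused by it alone meets the exclusion.

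**2. Does section 9.2.1 bring the event back?** It requires reporting whatever the suspected cause, but only of SAEs and AESIs. An event that section 9.1.2 has already declared not to be an SAE does not enter that sentence unless it is an AESI. The same holds for the provision on late related events, which also speaks of SAEs and AESIs.

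**3. Does the AESI list bring it back?** In part. The list in section 9.2.2 includes pneumonitis, grade 3 or higher hypoxia or dyspnoea, cardiac disorders of grade 2 or higher, colitis, hepatitis, pancreatitis, myelitis and severe cutaneous reactions. It does not include oesophagitis, fistula, ulceration of stomach or bowel, proctitis or rib fracture. The protocol anticipates these as SABR toxicities: oesophagitis in section 5.3.1, the others as avoidance endpoints in the organ-at-risk table of Appendix 1.

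**4. What does the word *exclusively* leave in?** Atezolizumab starts before progression and is continued through the second course. An event possibly related to atezolizumab, or to the combination, is not due only to treatment of progression and remains an SAE. The clause therefore bites only on events attributed to the second SABR course alone.

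**5. Which outputs lose the event?**
- Expedited reporting (section 9.2.1): lost.
- Sponsor assessment (section 9.3): the pharmacovigilance unit assesses seriousness, relationship and expectedness of SAEs, and SUSARs are drawn from them. An event that the site attributes to SABR alone and does not send is never given that second causality assessment. Whatever the annual safety report takes from SAEs lacks it too.
- SAE summary (section 8.3.3): lost.
- All-AE and grade 3/4 tables, deaths and discontinuations (section 8.3.3): kept, because the AE definition in section 9.1.1 has no such exclusion.

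**6. How many patients are exposed to the clause?** Section 8.1 assumes that up to 50% of patients in these cohorts will have oligoprogression: 0.5 × 54 evaluable = 27 and 0.5 × 60 enrolled = 30. This agrees with its stated 25 to 30 per cohort. Over two cohorts:
- 2 × 25 = 50 to 2 × 30 = 60 patients;
- 50/120 = 42% to 60/120 = 50% of the 120 planned lung cancer and sarcoma patients;
- 50/187 = 27% to 60/187 = 32% of the 187 planned in section 8.1.

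These are patients to whom the clause could apply, not events lost. The protocol gives no rate of serious SABR-only toxicity.

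**The case against.** The strongest reply is that the clause has a more natural reading. SABR at first progression is described under the study treatments, the reporting window is tied to study drug or treatment, and section 3.2 separately allows other anticancer therapy during follow-up. Such therapy can fall within the 90 days, so the exclusion has an ordinary purpose: to keep toxicities of non-protocol therapy out of the SAE data. This is probably what was meant. But section 9.1.2 does not say it, and it is the definition that investigators apply. The agreement of the other sections with that intent is a reason to write it down.

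The limits on scope do stand. A reader might infer three stronger things that the protocol does not support:
- *That the serious toxicities of the second course as a whole fall outside SAE reporting.* The word *exclusively*, the continued atezolizumab and the AESI route all prevent this.
- *That the data answering the second-course objective are removed.* The objective is framed in CTCAE grades, section 7.2.2 defines toxicity as graded adverse events at least possibly related to treatment, and those events stay in the AE data.
- *That the DSMB cannot see the events.* Section 9.4 does not restrict the board to SAEs, and section 13.1 plans for eCRF data to be ready before each of its meetings.

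Nor can one compute how far the SAE table would understate risk. That would need an assumed event rate, plus the assumption that every site excludes every event.

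**Conclusion.** Section 9.1.2 is wrong as written, within a narrow scope. Followed literally, it lets a serious toxicity attributed only to the second SABR course, and not listed as an AESI, be classed as not an SAE. The event then drops out of expedited reporting, of the sponsor's SUSAR assessment and annual-report material that start from SAEs, and of the SAE summary. This conflicts with the secondary objective on second-course safety and with a reporting window tied to study drug or treatment.

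By the protocol's own expectation 50 to 60 patients are exposed to the clause. How many events it affects is unknown and depends on how sites attribute cause and read the bullet. The conclusion assumes only that some investigators apply the text literally. That accrual is closed does not settle the matter, because events already classed under the bullet can still be recovered.

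**What to change.** Replace the first exclusion in section 9.1.2 with wording to this effect: *An event is not an SAE if its only cause is the tumour progressing, or an anticancer therapy given outside this protocol. Any event at least possibly related to protocol treatment, including the second SABR course and atezolizumab continued after progression, follows the normal SAE rules.*

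Send sites a short letter explaining the change. Ask them to check hospitalisations and other serious events after a second SABR course that were classed under this bullet, and to report those that qualify.

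The cost is an amended bullet, the letter and a look-back over at most the patients who received a second course. The SAE count may rise slightly. No treatment, endpoint or analysis changes.
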